6. STUDY PROCESS

6.1 INTERVENTIONS

All participants will complete three (3) group training sessions per week (total 20 weeks), under the supervision of trainers. Each session will last approximately 90 minutes and will be comprised of 30 minutes cognitive training (CT) or control cognitive training (cCT) followed by approximately 60 minutes of combined aerobic and progressive strengthening exercise (E) or control tone-stretching exercise (cE) and. All participants will receive a vitamin D (tablet 10,000 IU) or placebo three times per week.

Within each small group of up to eight individuals, participants follow the program tailored to their individual functioning level, with constant monitoring by the trainers. Participants are expected to attend all training sessions and research staff will strongly encourage them to do so. Each training group will have 1-2 trainers present each session to ensure a ratio of one (1) trainer per four (4) participants. To

avoid potential imbalances in exposure time, control interventions for exercise and cognitive training will have the same duration.

Throughout the 12 month trial, participants will be provided with falls calendars, in which they will record any falls that have occurred, and they will be asked to bring them at the training sessions. At the completion of the 20-week intervention, participants are not given ongoing access to the training. During follow-up, participants will be called three months after their completion of the intervention to track incidence of falls, adverse outcomes, such as emergency room visits and change of medications; physical activity will be also be tracked using the Physical Activity Scale for the Elderly (PASE). Following assessments at 6 and 12 months, participants will receive a compensation of \$50 for their participation for a total of \$100.

6.1.1 COGNITIVE TRAINING (MULTIMODAL CT-INTERVENTION)

Cognitive Training (CT) intervention will involve tablet-based multimodal and multi-domain dual-task training with memory load. The training uses the custom-written program, developed for neuro-rehabilitation and used in previous research trials for cognitive [32-34] and mobility outcomes [11]. Training sessions will take place in groups of up to eight participants before each of the fitness-training session for duration of 30 min max. Participants will perform a concurrent visuo-motor task (dual-task combination) composed of different sets of visual stimuli that have to be identified by tapping designated figures on an iPad (or an Android tablet). Participants will perform discrimination tasks involving sets of items (e.g. letters, numbers, animals, vehicles, fruits, celestial bodies). Each session will involve two sets of items, one for each task. The combination of sets of items will change every four sessions.

Task instructions will always be administered by a trained Research Assistant. Within each training session and for each task combination, participants will complete a first block of single-pure (SP) trials followed by mixed-trial blocks with single-task trials (SM) intermixed and dual-mixed trials (DM: 2 tasks at once). Each training session will involve 80 SP, 128 SM and 192 DM trials (thus 40% of the DM blocks will be SM trials). Within the DM trials, the first 30 training sessions will be performed following a fixed priority instruction (participants will be asked to keep an equal priority on left and right hands.) The following 30 sessions will be performed following a variable priority instruction (participants will be told to vary priority from one hand to another in different blocks). Participants will complete a total of 60 sessions. Importantly, an adaptive continuous feedback on performance was will be provided during the dual-mixed block of the training sessions.

Feedback will take the shape of a speedometer whose indicator moves and changes colour (green, yellow, orange or red) to inform participants of their response speed. Two speedometers (one for each hand) will be displayed at the top of the screen. Each speedometer is associated to one task. In equal priority blocks, participants will be asked to try to maintain both speedometers at least in the yellow zone and prevent them from turning to red. In variable priority blocks, participants will be asked to maintain the speedometer associated to the prioritized task in the green zone, while the other speedometer can be at least in the orange zone. The colour of the speedometers will be determined by the average reaction time (RT) on the last three trials' RT for the DM block compared to the median RT for the SM trials multiplied by a factor of 1.5 (for the first training session, as there are no previous SM trials, the DM block will be compared to 1500ms). In addition, a feedback will be provided at the end of the session, where participants will be informed of mean RT and accuracy achieved throughout sessions (presented in a histogram without explicit values).

6.1.2 EXERCISES (MULTIMODAL EXERCISE – INTERVENTION)

The exercises training program involves 3 weekly sessions of approximately 60 min each. All sessions will be held in appropriate gym facilities and take place between Monday and Friday ensuring that there are not three consecutive days (i.e. training can occur on Monday, Wednesday and Friday or Monday, Thursday and Friday etc.). Staff with experience and/or certification in exercises (graduate student in kinesiology, Canadian Society of Exercise Physiology certificates, etc.) will supervise all training sessions with at least one coach per four participants.

After a general warm-up, participants will execute the strength-training portion by performing light strengthening exercises (pushes and pulls using elastic bands, chair stands, and forward lunges). The next phase will include the following exercises: leg press, leg flexion (lower body), seated press, seated row, and seated pull (upper body). These exercises are made in a circuit alternating between lower and upper body exercises. A list of suggested exercises base on muscle groups will be provided to the trainers (see appendix II). The recovery period between exercises corresponds to the time needed to move from one station to another. While the first portion of this training protocol (12 weeks) will be dedicated to strength endurance exercises the following 12 weeks will focus on maximal strength. Training volume and intensity are described in the table below. Sets represent the number of circuit rounds while repetitions are maximal, which means that the resistance must be adjusted by the trainer so that the participant reaches exhaustion at the last prescribed repetition of each set. Training prescription for all exercises is made in accordance to the American College of Sport Medicine (ACSM) guidelines for strength development in older adults (ACSM, version 1998).

Weeks	Sets			Repetitions			Rest between sets (sec)
	Day 1	Day 2	Day 3	Day 1	Day 2	Day 3	
1-4	2	2	2	15-18	15-18	15-18	30
5-8	3	2	3	12-15	12-15	12-15	30
9-12	3	2	3	10	10	10	60
13-16	2	3	2	8	12	8	60
17-20	3	2	3	6	8	6	60

Following the strength portion of each session, an aerobic training will be prescribed. Participants will be asked to complete 10-20 minutes of cardiovascular exercises using different ergometers (treadmill, elliptical machines, cycling ergometers, rowing machines etc.), using steps or other forms of free aerobic exercises, as long as the cognitive load is minimized. Intensity will be monitored using a Borg scale (0-10) and the target will correspond to 5-6 for the first month, 6-7 for the second month and 7-8 for the last month. Details of the aerobic training are presented in the table below. Each session will end with a five (5) minute recovery period, which will consist of different breathing exercises and stretching.

Weeks	Sets	Duration (min)	Intensity (Borg 0-10)	Rest between sets (minutes)
1-4	2	10	5-6	1
5-8	2	10	5-6	1
9-12	2	10	6-7	1
13-16	2	10	6-7	1
17-20	2	10	7-8	1

Overall rate of perceived exertion (RPE) will be monitored using a Borg scale (0-10) 30 minutes after the end of each session. Participants will have to rate the overall difficulty of the training session. These results will provide information about the training load (session RPE – sRPE), monotony and strain.

6.1.3 VITAMIN D SUPPLEMENTATION

Participants will receive Vitamin D supplementation (1 tablet of 10,000IU of Vitamin D₃) or matching placebo three times per week in order to reach a weekly cumulative dose of 30,000 IU per week (equivalent of 4,258 IU daily). The vitamin D capsules will be provided by the Research Coordinator

(RC) in vials at baseline assessment and every four weeks to complete 5 vials during the training period. Vials will be returned by the participants to the RC at the end of each 4 weeks block. Rationale and bio-safety of the dose: The dose of 10,000 IU/day is currently approved by Health Canada as a supplementation for elderly patients. Heaney et al. have administered doses of 30,000 IU/day Vitamin D₃ to adult men for five months, with no significant changes in serum calcium concentrations or adverse reactions.[35-37] A comprehensive review of toxic effects of vitamin D found that the lowest level at which an adverse effect was observed was a serum calcidiol concentration of 200 nmol/l, corresponding to a daily intake of 40,000 IU. Therefore, three weekly doses of 10,000IU have a 9-fold weekly margin of safety of the established safe dose.

6.2 CONTROL/PLACEBOS

6.2.1 Control Cognitive Training

The active control cognitive training group will participate in skills training courses based on a published study from our research group[38]. Each session will consist of Internet search for 3 hotels, 3 touristic places and 3 restaurants, of participant's preference, in cities determined by the instructor at the beginning of each training session (a list of cities is presented in the manual of procedures for cognitive training). Another task will be watching a 20 minutes National Geographic documentary movie selected by the instructor at the beginning of each session; at the end of the movie participants need to answer three questions about the watched movie. These iPad tasks will be alternated between sessions to prevent boredom. The approximate time to perform both tasks is 20 minutes which is the approximate time to complete the dual-task training on the iPad.

Active control sessions will be held in groups of up to 8 participants and will take place in the same context and physical environment used for dual-task training sessions and lead by the same instructors. Studies compared dual-task training to single-task training, as a control condition, in order to control for exposure of the same specific tasks performed separately [38]. However, it can be argued that single-task training is not engaging or stimulating enough and does not provide a feeling of progression. In response to this, Walton et al. [39] recommended that cognitive training studies use preferably sham trainings whereby clinician interaction and participant expectation effects can be reliably matched. Therefore, this study will compare dual-task training to a non-specific intervention, more comparable to cognitively stimulating activities that older adults can naturally engage in. To assure same time exposure and same social interaction than in active intervention, the control intervention will be held in groups using the same type of device that is used for the active intervention.

6.2.2 Placebo Vitamin D supplementation

Participants will receive Vitamin D supplementation (1 tablet of 10,000IU of Vitamin D₃) or matching placebo three times per week in order to reach a weekly cumulative dose of 30,000 IU per week (equivalent of 4,258 IU daily). The vitamin D capsules will be provided by the Research Coordinator (RC) in vials at baseline assessment and every four weeks to complete 5 vials during the training period. Vials will be returned by the participants to the RC at the end of each 4 weeks block. Rationale and bio-safety of the dose: The dose of 10,000 IU/day is currently approved by Health Canada as a supplementation for elderly patients. Heaney et al. have administered doses of 30,000 IU/day Vitamin D₃ to adult men for five months, with no significant changes in serum calcium concentrations or adverse reactions.[35-37] A comprehensive review of toxic effects of vitamin D found that the lowest level at which an adverse effect was observed was a serum calcidiol concentration of 200 nmol/l, corresponding to a daily intake of 40,000 IU. Therefore, three weekly doses of 10,000IU have a 9-fold weekly margin of safety of the established safe dose.

6.2.3 Control Exercises (Tone-Stretching Exercises)

Participants assigned in the control exercise condition will take part in tone-stretching sessions in groups of up to 8 participants, supervised by a trainer. The exercises will be devoted to improve muscle tone, flexibility, without improving, strength, cardiorespiratory capacity (and mobility). Resistant load and number of repetitions will not progress across exercise sessions. The session will start with a 5-minute warm-up on the machine of their choice. This will be followed by 50 minutes of stretching exercises that will target the entire body, one joint at a time, from head to toes. Exercises will be performed in a seated position as much as possible. The stretching program will be based on the one developed by Stanziano et al.[39] The session will end with 5 minutes of relaxation. Variability in exercises performed between sessions will be encouraged in order to avoid progression throughout the entire program.

6.3 Supervision

All physical exercise training will be fully supervised by research assistants trained in exercise physiology or with kinesiology or physical therapy backgrounds or training. Training frequency is 3 days/week. Each session will take 90 minutes on average.

7.0 STUDY PROCEDURES

Baseline measurements will be obtained prior to randomization. There will be three measurement sessions: baseline, 6 months, and 12 months (Figure 1, Appendix I). Outcomes will be assessed by

trained assessors blinded to group allocation. As outlined in point 5, there are five main interventional/assessment centers. Recruitment will be occurring primary in clinics serving MCI populations already identified in each site and from the community. In addition, older persons belonging to the community will be invited to participate through different recruitment methods, including case findings by phone interviews and recruitments in primary care and geriatrics clinics. Strategies to increase the awareness of the study will be implemented through explanatory brochures and a dedicated webpage: “www.synergictrial.com”. Results of the mobility tests and laboratory examinations can be provided to the participant and to her/his family physician upon their request. Transportation will be paid when necessary. Finally, dissemination of our findings will be conducted in the community through open discussion sessions and booklets and publications in the local newsletter.

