5. Pre-existing or current active participation in physical activity program involving aerobic or resistance training regimen in previous 6 months.
6. Taking Cognitive enhancers, Neuroleptics, Anticholinergics, or Vitamin D in doses more than 1000IU/day or equivalent.
7. Known hypercalcemia and/or disorder that is cause of hypercalcemia (e.g. hyperparathyroidism/ Paget's disease/ Sarcoidosis).
8. Known renal/kidney insufficiency.
9. Uncontrolled hypertension.
10. Uncontrolled diabetes.

5.3 SAMPLE SIZE:

Sample size calculation is based on changes in our main primary outcome: stabilization/improvement in cognition as measured using the **Alzheimer Disease Assessment Scale Cognitive Plus** (ADAS-Cog Plus). We expect a change of three (3) points on the ADAS-Cog Plus scores, a value that is considered clinically significant, and it is similar in magnitude to the improvements seen in positive pharmacological clinical trials in dementia.[26] Two previous studies testing the effect of exercises on cognition in 200 MCI participants shown a mean score of 6-7 and a standard deviation of 3 in the ADAS-Cog.[24,31] Based on these data and assuming a mean change of 3 points in the ADAS-Cog, 34 participants per arm are required to have 80% power to detect a change of three points or more on the ADAS-Cog with a 2-tailed α error of 5%, adjusted for 10 potential pairwise comparisons. We estimate a worst case scenario of 15% of dropout rate during the 20 weeks of follow up to the main endpoint. Therefore, we will aim to recruit 40 per arm for a total of 200 participants.

Sample size estimates per group for the primary outcome: change in ADAS-Cog Plus

	Type I error=0.05	Type I error=0.01	Type I error=0.001
Power=80%	34	50	59
Power=90%	51	54	70
Power=99%	68	82	102

Reference: Independent Groups - Machin D, Campbell M, Fayers, P, Pinol A (1997) Sample Size Tables for Clinical Studies Second Ed. Blackwell Science ISBN 0-86542-870-0 p. 24-25

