7.2.2 BLINDING

In order to minimize a source of bias, this trial is planned to be a double-blinded study. Research personnel performing the outcome assessments will be blinded to group allocation. Participants will be blinded of intervention.

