7.6.3 Blood Biomarkers

The following biomarkers will be drawn at the Baseline Visit, Visit 3 and Visit 4:

- Vitamin D levels, Calcium, PTH, and lipid level will be measured by conventional methods.
- Serum High Sensitive CRP, IL-6, BDNF, and VEGF receptor 1, IGF-1 will be determined by standardized ELISA methods

Blood samples for this study (completed at baseline and 6-month visit) will be done by a certified study Research Coordinator or Research Assistant. Participants will be asked to fast and will be provided with a small breakfast after the draw is complete. Samples will be collected, processed and stored securely at the respective site in a -80C freezer used for research purposes. Samples will be batch shipped securely to a centralized laboratory for analysis. Sample tubes will be labeled appropriately by the Study Coordinator with only the participant's unique study identifier and time point of collection.

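### Vitamin D and PTH results can be released on request with no embargo, so a month-6 value can reveal the vitamin D allocation before the month-12 assessment

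*Combined protocol and SAP*

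**What the plan says.** - **Release of results.** Protocol section 7.0: "Results of the mobility tests and laboratory examinations can be provided to the participant and to her/his family physician upon their request". No analyte is excepted and no waiting period is given.
- **What is measured.** Section 7.6.3: "Vitamin D levels, Calcium, PTH, and lipid level will be measured by conventional methods".
- **When.** The same section: "The following biomarkers will be drawn at the Baseline Visit, Visit 3 and Visit 4". Visits 3 and 4 are months 6 and 12, and Appendix I agrees. A later parenthesis in 7.6.3 and SAP Table 1 show blood draws at baseline and month 6 only.
- **Handling.** Section 7.6.3 has samples frozen at each site, and then: "Samples will be batch shipped securely to a centralized laboratory for analysis". No batch dates are given, and nothing links batching to release.
- **Order.** Section 7.0: "Baseline measurements will be obtained prior to randomization".
- **Blinding.** Section 7.2.2: "Participants will be blinded of intervention". Laboratory results are not mentioned there.
- **Dose contrast.** Section 6.1.3 gives active tablets "in order to reach a weekly cumulative dose of 30,000 IU per week", against matching placebo.
- **Non-study vitamin D.** Section 5.2 excludes at entry those "Taking Cognitive enhancers, Neuroleptics, Anticholinergics, or Vitamin D in doses more than 1000IU/day or equivalent". Sections 6.1.3 and 9.3 do not address vitamin D started after entry. The last line of section 9.1, as written, calls for different vitamin D analogues to be given together.

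**The concern.** Vitamin D against matching placebo is the part of this trial where participant blinding is most achievable, because exercise and cognitive training are visible to those who do them. Serum vitamin D is a direct marker of that allocation. A rule that gives the value to the participant and the family physician on request provides a way around the blind, and following the protocol as written is enough to use it.

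Three things are at stake:

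- the credibility of month-12 outcomes that depend on what participants believe they received, mainly SF-36, GDS-30 and GAD-7;
- supplement use after month 6, which would then depend on allocation and would affect the long-term comparison in SAP 10.2.5;
- to a lesser and unknown degree, the month-6 vitamin D contrast in SAP 10.2.3 (arms 1 and 3 against arms 2 and 4), if baseline results prompt supplementation during the intervention.

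**Working it through.** The plan states no figure on this point, so the main check is to follow each blood sample through the schedule.

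**Step 1. Baseline sample.** It is drawn before randomization (sections 7.0 and 7.2.1). It carries no information on allocation, and low values should be balanced across arms. If it is returned during the 20 weeks, a participant or family physician could start vitamin D. With participants blinded, this is expected about equally in all arms.

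**Step 2. Month-6 sample.** It is drawn at Visit 3, after the intervention and at the same visit as the primary endpoint (section 7.3; SAP section 5). Its result comes too late to influence the month-6 ADAS-Cog. Set beside the baseline value, it can indicate allocation. From release until Visit 4 the participant may be unblinded, and those who infer placebo may start vitamin D.

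**Step 3. What limits this.** Freezing and batch shipment may delay results, but no date or release rule makes the delay a safeguard. The 1000 IU/day limit applies at entry only. The per-protocol analysis is named in protocol section 8 and SAP 10.2 but not defined.

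**Step 4. How many.** SAP section 7 allows 15% attrition: 200 × 0.85 = 170 expected month-6 completers. The placebo side of the vitamin D contrast has 2 × 40 = 80 randomized and 80 × 0.85 = 68 expected completers. Virtual visits under the pandemic amendments collect no blood and lower the number with results further.

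**Step 5. Illustration of dilution by the baseline route.** Inputs: d = 0.5 and 15% attrition (SAP section 7), two-sided 0.05 (SAP 10.2), 68 per side. Let p be the share who start off-trial vitamin D in each arm, g0 their gain if on placebo and g1 their gain if already on active. Then

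observed d = 0.5 − p × (g0 − g1).

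If extra vitamin D helps both sides equally, g0 = g1 and nothing is lost. The upper bound takes g0 = 0.5 and g1 = 0, so observed d = 0.5 × (1 − p). Power is from the noncentral t with 68 + 68 − 2 = 134 degrees of freedom and noncentrality d × √(68/2), holding the standard deviation fixed.

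| p (assumed) | Observed d | Noncentrality | Power |
|---|---|---|---|
| 0% | 0.500 | 2.915 | 82.5% |
| 5% | 0.475 | 2.770 | 78.5% |
| 10% | 0.450 | 2.624 | 74.1% |
| 20% | 0.400 | 2.332 | 63.9% |

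If placebo supplementers gain half the effect (g0 = 0.25, g1 = 0), observed d = 0.5 × (1 − p/2), and power is 80.6%, 78.5% and 74.1% for p = 5%, 10% and 20%. A normal approximation gives values less than one percentage point higher (83.0% at p = 0). The starting value is consistent with the SAP's planned 80%. The documents give no basis for choosing p.

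**The case against.** The strongest reply is that practice will protect the blind. Samples are frozen and analysed centrally in batches, so results may not exist until well after a participant finishes. That may prove true, but the protocol does not say so, and section 7.0 offers results without that condition. The consent pages were not available for this review, so a limit stated there cannot be ruled out.

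Four further points stand and narrow the finding:

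- A reader might infer that baseline results drive supplementation mainly in the placebo arms. The documents do not support this, because the baseline draw precedes randomization and participants are blinded.
- A reader might infer that release of month-6 results threatens the primary endpoint. It does not, because that blood is drawn at the endpoint visit.
- A reader might infer that a null vitamin D result could not be told apart from contamination. Serum vitamin D is measured before and after intervention (SAP 9.5), so lost separation between arms should show. Medications are recorded in the Clinical Medical Questionnaire (section 7.6.1), and medication changes at the phone call three months after the intervention (section 6.1).
- SAP 10.2.5 concerns ADAS-Cog scores, which are performance tests given by blinded assessors and so are less open to expectation than self-report. SF-36, GDS-30 and GAD-7 are collected at month 12 (section 7.5), but SAP section 9 does not list them as secondary outcomes, although protocol section 4.2 includes quality of life.

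**Conclusion.** The gap is real on the text. An open release rule, an analyte that marks allocation and a promise of participant blinding stand together with nothing to reconcile them. Its main effect is on months 6 to 12: possible unblinding to vitamin D, possible bias in self-reported outcomes, and allocation-dependent supplement use before the month-12 comparison. The month-6 ADAS-Cog endpoint is not exposed to unblinding by this route.

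The baseline route can touch the month-6 vitamin D contrast only if results are requested, returned and acted on within 20 weeks, and only so far as placebo participants gain something the active arms already have. The size of both effects is unknown, because the documents give no request rate, no supplementation rate and no expected vitamin D level by arm. The power figures are an upper-bound illustration, not an estimate. This is an inexpensive protection worth adding, not a defect that undermines the primary analysis.

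**What to change.** **Protocol section 7.0.** Exclude 25-OH vitamin D and PTH from results released on request until that participant's month-12 visit is complete. Withhold them from outcome assessors and trainers for the same period. Send safety-relevant values to a site physician who is not an assessor, with the clinical response left to the investigators.

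**SAP 10.2.** Keep intention-to-treat as primary. Add a supportive sensitivity analysis for off-trial vitamin D use, based on the medication data already recorded. Do not rely on a per-protocol exclusion: supplement use after randomization may depend on allocation or prognosis, so removing those participants can itself introduce bias.

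**Consistency.** Reconcile exclusion criterion 6 in section 5.2 with the last line of section 9.1 on non-study vitamin D. Make section 7.6.3, Appendix I and SAP Table 1 agree on whether blood is drawn at month 12.

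**Cost.** A short addition to section 7.0, one sentence in the SAP, a matching line in the information letter if needed, and a small routing step for safety values. Participants wait longer for two laboratory values. If follow-up is already complete, the sensitivity analysis is still feasible, and the report can state how many vitamin D or PTH results were released, to whom and when.
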